#### 5.2 EXCLUSION CRITERIA

An individual who meets any of the following criteria will be excluded from participation in this study:

1. Daily corticosteroids at a dose equivalent to Prednisone 20 mg/day or greater during the period two weeks before enrollment to the trial. *Intermittent* steroid dosing at or above this level is permitted (i.e., weekly dexamethasone dosing as part of myeloma therapy)
2. History of previous severe reaction to any available COVID-19 vaccine (defined as any Grade 3 or higher reaction)
3. Febrile illness within 3 days of booster dosing.
4. Documented SARS-CoV2 infection within 2 weeks of enrollment.
5. Less than 3 months post-autologous or allogeneic stem cell transplant (NOTE: transplant between initial standard vaccine administration and enrollment is NOT otherwise grounds for exclusion from participation).

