## 1.2 SCHEMA

### ***Flow diagram***

### 1.3 SCHEDULE OF ACTIVITIES (STUDY CALENDAR)

Procedures	Screening/Consenting Day -14 to -1	Enrollment/Baseline Visit 1, Day 1	Days 2-8, 15, 22 (+/- 1 day) Phone/Text/Email	Study Visit 2 Day 28 +/- 3 days
Informed consent	X			
Demographics	X			
Medical history update	X			X
Administer vaccine dose		X		
Concomitant medication review	X			X
Physical exam	X			X
Vital signs	X	X		X
Height	X			
Weight	X			X
Performance status f	X			X
Hematology a	X			X
Serum chemistry b	X			X
Cardiac Biomarkers e	X		(X) d	X
Coagulation testing c	X			
Anti-SARS-CoV2 IgG Ab titer	X			X
Patient-reported AE assessment		X	X---X	X
Correlative blood sample collection	X			X

a. CBC with diff  
b. standard CMP, uric acid, magnesium, phosphorus, LDH, quantitative immunoglobulins (IgG, IgA, IgM)  
c. PT/INR, PTT, fibrinogen  
d. only if patient reports chest pain, palpitations, shortness of breath, or other symptoms suggesting cardiac etiology  
e. hsTrop I and BNP  
f. See Appendix 1: ECOG Performance Status

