### 3 OBJECTIVES AND ENDPOINTS

OBJECTIVES	ENDPOINTS	JUSTIFICATION FOR ENDPOINTS
Primary		
To determine whether booster dosing with the Moderna COVID-19 vaccine can induce humoral immune responses in patients with hematologic malignancies who did not have an adequate response to prior first vaccination with any of the SARS-CoV2 vaccines authorized for use in the USA.	The primary endpoint is the observed rate of anti-SARS-CoV2 IgG antibody seroconversion (from negative to positive) measured 28 days (+/- 3 days) following a booster dose of the Moderna COVID-19 vaccine.	The described assay measures antibodies against the SARS-CoV2 spike protein, which is what the Moderna vaccine is designed to induce. This is a commercially available assay which is already in use at the Karmanos Cancer Center and Detroit Medical Center.
Secondary		
1. To determine whether booster dosing with the Moderna COVID-19 vaccine is safe in patients with multiple myeloma, AL amyloidosis, or other hematologic malignancies.  2. To compare the humoral immune responses between the patients who had a WEAK POSITIVE RESPONSE to prior vaccine (Cohort 3) vs. those with NO RESPONSE to prior vaccination (Cohorts 1 and 2).  3. To descriptively summarize clinical and immune characteristics which contribute to likelihood of	1. AEs and SAEs observed in participants, determined according to daily phone calls or video chats for 1 week following vaccine administration, and then weekly after that until 4 weeks after vaccination (Pts will also be examined 4 weeks after vaccination).  2. Humoral immune responses measured 28 days (+/- 3 days) following a booster dose of the Moderna COVID-19 vaccine.  3.a. Clinical characteristics of enrolled participants, including treatment history, disease, status, or presence	This is an early experience with booster dosing using the Moderna COVID-19 vaccine. Though new AEs/SAEs are not expected, it is important to document the safety of this intervention.  Clinical factors related to disease or immune status may be associated with likelihood of responding to booster

OBJECTIVES	ENDPOINTS	JUSTIFICATION FOR ENDPOINTS

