### 5 STUDY POPULATION

#### 5.1 INCLUSION CRITERIA

In order to be eligible to participate in this study, an individual must meet all of the following criteria:

1. Provision of signed and dated informed consent form
2. Stated willingness to comply with all study procedures and availability for the duration of the study
3. Male or female, aged 18 years of age or older
4. Previously diagnosed with MM/AL amyloidosis (Cohorts 1 or 3) or other hematologic malignancy (Cohorts 2 or 3).
5. Previously received any one of the available COVID-19 vaccines (between 4 and 36 weeks prior to enrollment)
6. Anti-SARS-CoV2 IgG antibody titer of results less than 1.0 units (Cohorts 1 and 2), or 1.0-1.99 units (Cohort 3). Antibody titers will be measured within 14 days of enrollment.
7. If currently receiving potentially immunosuppressive anti-neoplastic therapy for their underlying hematologic condition, a two-week interruption in therapy before and after the booster dose of vaccine is ENCOURAGED BUT NOT REQUIRED (physician discretion).

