### 5.3 LIFESTYLE CONSIDERATIONS

Patients who are diagnosed with an acute SARS-CoV2 infection in the post-vaccine follow-up period (i.e., between the vaccine and the serologic testing for response to vaccine) will be considered non-evaluable for the primary endpoint of the trial.

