### 6.2.2 FORMULATION, APPEARANCE, PACKAGING, AND LABELING

Moderna COVID-19 Vaccine is provided as a white to off-white suspension for intramuscular injection. Each 0.5 mL dose of Moderna COVID-19 Vaccine contains 100 mcg of nucleoside- modified messenger RNA (mRNA) encoding the pre-fusion stabilized Spike glycoprotein (S) of SARS-CoV-2 virus.

Each dose of the Moderna COVID-19 Vaccine contains the following ingredients: a total lipid content of 1.93 mg (SM-102, polyethylene glycol [PEG] 2000 dimyristoyl glycerol [DMG], cholesterol, and 1,2-distearoyl-sn-glycero-3-phosphocholine [DSPC]), 0.31 mg tromethamine, 1.18 mg tromethamine hydrochloride, 0.043 mg acetic acid, 0.20 mg sodium acetate trihydrate, and 43.5 mg sucrose.

Moderna COVID-19 Vaccine does not contain a preservative.

The vial stoppers are not made with natural rubber latex.

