### 7.2 PARTICIPANT DISCONTINUATION/WITHDRAWAL FROM THE STUDY

Participants are free to withdraw from participation in the study at any time upon request.

An investigator may discontinue or withdraw a participant from the study for the following reasons:

- Significant study intervention non-compliance
- If any clinical adverse event (AE), laboratory abnormality, or other medical condition or situation occurs such that continued participation in the study would not be in the best interest of the participant
- Documented SARS-CoV2 infection
- If the participant meets an exclusion criterion (either newly developed or not previously recognized) that precludes further study participation
- Participant unable to return for post vaccination assessment at 28 days (+/- 3 days) after vaccination. NOTE: patients who miss this window but are able to return to complete required assessments may be able to remain on trial (treating physician must discuss with the PI).

The reason for participant discontinuation or withdrawal from the study will be recorded on the Case Report Form (CRF). Subjects who sign the informed consent form and are enrolled but do not receive the study intervention may be replaced. Subjects who sign the informed consent form, and receive the study intervention, and subsequently withdraw, or are withdrawn or discontinued from the study, will be replaced.

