### 8.2 SAFETY AND OTHER ASSESSMENTS

Safety Assessments: participants will have a medical history, vitals, and physical exam and bloodwork for laboratory testing including cardiac biomarkers performed during screening and on day 28 (+/- 3 days). Participants will also be contacted by phone/text/email/video platform on days 2-8, 15, and 22 to document any AEs experienced. Any patients reporting chest pain, palpitations, shortness of breath, or other symptoms which in the opinion of the treating physician suggest cardiac etiology will be asked to have additional bloodwork done to measure cardiac biomarkers (hsTrop I, BNP).

**Baseline Patient characteristics:** The patient's chart in the EMR will be accessed to document general demographics, their hematologic diagnosis and the status of that disease, current and past treatment history for the underlying hematologic condition, other past medical history, medications, and baseline laboratory parameters (including but not limited to neutrophil count, lymphocyte count, immunoglobulin levels). These and other variables (TBD) will be entered into a CRF to be used for eventual univariate and multivariate analyses. Health Insurance Portability and Accountability Act (HIPAA) rules, other relevant federal or state laws, and local institutional requirements will be followed, as applicable.

Blood sample collection for future correlative testing (e.g., immune cell profiling, assessment of immune exhaustion, etc). The following samples will be collected and stored in [name]'s laboratory: **one 15 mL EDTA tube of peripheral blood** obtained prior to administration of the booster dose, and **a second 15 mL EDTA tube of peripheral blood obtained at the day 28 visit**. The first correlative testing we are planning to perform is a detailed anti-viral protein antibody evaluation using the Bio-Plex Pro SARS-CoV-2 Serology assay. This assay is a sensitive and specific method to monitor the antibody immune response profile against viral proteins. There are three isotype-specific 4-plex panels that measure antibodies against SARS-CoV-2 Nucleocapsid, Receptor Binding Domain, Spike 1, and Spike 2 viral proteins. The isotype-specific antibodies detected are IgA, IgG, and IgM. The viral-protein-coated beads can be used to assay antibodies in multiple species and only need to be paired with a species-specific biotinylated

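### Undiagnosed SARS-CoV-2 infection between the baseline titre and Day 28 can be scored as booster response, and the nucleocapsid result already planned is not used to check for it

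*Combined protocol and SAP*

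**What the plan says.** **Endpoint.** Section 3 states that "The described assay measures antibodies against the SARS-CoV2 spike protein". Section 9.3 counts a cohort as successful if at least 6 of 52 patients reach the 2.0 S/CO level, against a null of 5% or less and an alternative of 15%.

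**Infection rules.** There are three, and each depends on the infection having been recognised:
- Section 5.2 excludes "Documented SARS-CoV2 infection within 2 weeks of enrollment".
- Section 5.3 treats as non-evaluable for the primary endpoint "Patients who are diagnosed with an acute SARS-CoV2 infection in the post-vaccine follow-up period".
- Section 7.2 lists "Documented SARS-CoV2 infection" among the reasons for which an investigator may withdraw a participant.

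**Timing and testing.** Section 5.1 says "Antibody titers will be measured within 14 days of enrollment", and the calendar in section 1.3 heads that column "Screening/Consenting Day -14 to -1". The calendar lists no PCR, antigen or other infection test at any visit.

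**Analysis set.** Section 9.4.1 includes, within each cohort, everyone who received the booster and was sampled in the window. It does not repeat the section 5.3 rule.

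**Correlative assay.** Section 8.2 plans a Bio-Plex assay as the first correlative test, with blood drawn before the dose and again at Day 28: "There are three isotype-specific 4-plex panels that measure antibodies against SARS-CoV-2 Nucleocapsid, Receptor Binding Domain, Spike 1, and Spike 2 viral proteins". Section 6.2.2 describes the vaccine as "messenger RNA (mRNA) encoding the pre-fusion stabilized Spike glycoprotein (S) of SARS-CoV-2 virus". No eligibility, evaluability or response rule uses the nucleocapsid result.

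**The concern.** A spike titre cannot show whether the antibody came from the booster or from the virus. The trial has no control group, so nothing inside it shows how many patients would have crossed the threshold over the same weeks without a booster.

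The sponsor accepts the principle, because section 5.3 removes diagnosed infections from the primary endpoint. That rule finds only what is tested for outside the protocol. A mild, silent or untested infection passes through, and its antibody counts towards the six responders that each cohort needs. With a threshold that low, one such rise turns 5 of 52 into 6 of 52. The same rises enter the comparison of Cohort 3 with Cohorts 1 and 2.

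The trial plans to collect data that bear on this question but gives them no role in the primary conclusion.

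**Working it through.** **Inputs.** From section 9.3: 52 patients per cohort, success at 6 or more responders, null 5%, alternative 15%, one-sided 5% level, 80% power. The infection-driven share, a, is not in the documents and is an assumption shown as a range.

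**1. The plan's own figure.** With X binomial:
- P(X ≥ 6 | n = 52, p = 0.05) = 0.0445
- P(X ≥ 6 | n = 52, p = 0.15) = 0.812

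Both limits are met, and 52 is the smallest n that meets them. The sample size is correct.

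**2. Infection adds to the 5%.** Suppose 5% of patients convert for other reasons, and a share a of all patients, independently of that, gains a qualifying titre from infection. The scored response rate is

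p = 0.05 + 0.95 × a

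| Assumed a | Scored rate p | P(X ≥ 6 of 52) |
|---|---|---|
| 0 | 5.00% | 4.5% |
| 1% | 5.95% | 8.7% |
| 2% | 6.90% | 14.7% |
| 3% | 7.85% | 22.2% |

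At a = 2% the expected number of infection-driven rises is 52 × 0.02 = 1.04, about one patient per cohort.

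**3. The 5% already includes infection.** Section 9.3 words the null as a spontaneous rise, which can be read as covering every rise not caused by the booster. On that reading the relevant rate is total non-booster conversion:
- total 3%: P(X ≥ 6) = 0.5%
- total 5%: P(X ≥ 6) = 4.5%
- total 10%: P(X ≥ 6) = 42.1%

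The error rate holds while the total is at most 5% and fails above it. Section 9.3 gives no derivation of the 5% and does not say which reading is meant.

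**4. Effect of removing patients in a sensitivity analysis.** With the requirement kept at 6 responders:

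| n | P(X ≥ 6) at 5% | P(X ≥ 6) at 15% |
|---|---|---|
| 52 | 4.5% | 81% |
| 50 | 3.8% | 78% |
| 47 | 2.9% | 73% |

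Five responders would not do at these sizes: P(X ≥ 5) under 5% is 10.4% at n = 50 and 8.5% at n = 47. An exact test at the reduced n therefore still needs 6.

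**The case against.** **The null may already allow for this.** The spontaneous-rise wording fits infection, and adding infection on top of 5% could count it twice. This stands: neither reading can be settled from the documents, so both are shown above.

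**The share may be small.** To count towards a, a patient must be infected in roughly six weeks, go undiagnosed, reach the response threshold by Day 28, and be someone who would not have responded otherwise. These patients have already responded poorly to vaccination, and section 2.2 says such patients are less likely to mount a humoral response. This also stands. A reader might carry the table on to a = 5%, where the success probability is 39.7%, and take that as the trial's error rate. It would need about 52 × 0.05 = 2.6 such patients per cohort, and no document supports that.

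**Safeguards exist.** Febrile illness within 3 days of dosing is excluded, participants are contacted on Days 2–8, 15 and 22, and Day 28 includes a history and examination. These give symptomatic infection chances to surface. However, no SARS-CoV-2 test is mandated at any contact. What remains is mainly silent or untested infection.

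**Infection just before entry.** A reader might infer that a patient diagnosed just over two weeks before enrollment, with the qualifying titre drawn about a day later, is a proven route to a false response. The two windows do permit that sequence. But it is narrow, and it also requires seroconversion after the draw. The documents give no seroconversion time, so it is a matter for reconciliation only.

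**Other rival explanations.** A reader might call infection the main alternative explanation. The documents do not rank it. Optional therapy interruption, primary vaccination as recent as 4 weeks before enrollment, and Cohort 3 starting at 1.0–1.99 S/CO are others.

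**Conclusion.** The point holds as a gap in the analysis plan. Followed exactly, the plan can score an undiagnosed infection between the baseline titre and Day 28 as a booster response. Read alone, section 9.4.1 would also keep diagnosed infections that section 5.3 removes.

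The size cannot be fixed from the documents. Per cohort, the chance of a false success is 8.7% to 22.2% for an assumed infection share of 1% to 3% on top of 5%. It is at or below 4.5% if the 5% covers all non-booster rises and these total no more than 5%. The first figure rests on an assumed share and on independence; the second on a reading of the null that section 9.3 does not confirm.

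The documents do not show that the trial's error rate is in fact inflated, and the sample size is not in error. This is a cheap improvement: planned samples and a planned assay could address the question if the rule is written before results are seen.

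**What to change.** 1. **Section 9.4.1, analysis set.** Carry over the section 5.3 exclusion of participants diagnosed with infection between dose and serology, so that the two sections agree.
2. **Section 9.4.1, sensitivity analysis.** Pre-specify nucleocapsid IgG from the planned Bio-Plex run as an infection marker, with the positivity cut-off and the definition of newly positive fixed in advance. Repeat each cohort's primary test without participants newly positive at Day 28, as an exact binomial test against 5% at the reduced n. Repeat the Fisher comparison of Cohort 3 with Cohorts 1 and 2 on the same basis. Report participants who were nucleocapsid-positive at baseline separately. The primary test stays as planned.
3. **Section 9.3.** State whether the 5% null includes infection-driven rises, and where the 5% comes from.
4. **Sections 5.1 and 5.2.** The sponsor should reconcile the two-week infection look-back with the 14-day titre window. The choice of interval is the sponsor's.

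**Cost.** Protocol and SAP wording only, with no added visit, sample or assay. Power in the sensitivity analysis falls slightly, from 81% at n = 52 to 78% at n = 50 with 6 responders still required. The correction is partial: some patients may not make nucleocapsid antibody after infection, and a newly positive participant may also have responded to the booster. The result should be read beside the primary analysis and not in its place.

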### 5.3 LIFESTYLE CONSIDERATIONS

Patients who are diagnosed with an acute SARS-CoV2 infection in the post-vaccine follow-up period (i.e., between the vaccine and the serologic testing for response to vaccine) will be considered non-evaluable for the primary endpoint of the trial.

### 5.4 SCREEN FAILURES

Screen failures are defined as participants who consent to participate in the clinical trial but are not subsequently confirmed to be eligible to receive the study intervention or entered in the study. A minimal set of screen failure information is required to ensure transparent reporting of screen failure participants, to meet the Consolidated Standards of Reporting Trials (CONSORT) publishing requirements and to respond to queries from regulatory authorities. Minimal information includes demography, screen failure details, eligibility criteria, and any serious adverse event (SAE).

Individuals who do not meet the criteria for participation in this trial (screen failure) because of a febrile illness or other factor which has resolved may be rescreened at the discretion of the enrolling investigator. Rescreened participants should be assigned the same participant number as for the initial screening.]

### 5.5 STRATEGIES FOR RECRUITMENT AND RETENTION

Potential participants will be identified from amongst the hematologic malignancy patients seen at the Karmanos Cancer Institute. Post-vaccination anti-SARS-CoV2 IgG Ab testing is being conducted as part of routine clinic practice at the cancer center, so many patients meeting eligibility criteria are already identified. We anticipate the majority of participants will be enrolled within a month of the trial opening. We also anticipate that patients may be referred for participation from within the McLaren Network or from other hospital networks, or they may self-refer. We also plan to inform myeloma, amyloidosis, and hematologic malignancy patient support groups across the state of Michigan using IRB-approved communications. African American patients who have previously received any of the available COVID-19 vaccines are having anti-SARS-CoV2 IgG Ab titers checked at the same frequency as other patient populations, and thus will have equal opportunity to participate in this trial. There is no compensation provided for participating in this trial.

## 6 STUDY INTERVENTION

### 6.1 STUDY INTERVENTION(S) ADMINISTRATION

#### 6.1.1 STUDY INTERVENTION DESCRIPTION

All participants in each of the cohorts will receive a single dose of the Moderna mRNA COVID-19 vaccine. This is an open label, non-randomized trial.

#### 6.1.2 DOSING AND ADMINISTRATION

The dose of Moderna mRNA vaccine to be administered is the same for all patients in all enrollment cohorts: 0.5 mL administered intramuscularly as a single dose, according to the manufacturer's package insert.

## 6.2 PREPARATION/HANDLING/STORAGE/ACCOUNTABILITY

### 6.2.1 ACQUISITION AND ACCOUNTABILITY

The Moderna mRNA COVID-19 vaccine product to be used in this trial will be obtained from the McLaren Network Pharmacy Department. The product will be transferred to the Karmanos Cancer Institute's Investigational Pharmacy for dispensation to trial participants. As the vaccine is supplied in multi-dose vials, there will be sustained effort to schedule trial participants in such fashion as to minimize wastage of any doses. Unused product will be discarded according to standard pharmacy operating procedure.

### 6.2.2 FORMULATION, APPEARANCE, PACKAGING, AND LABELING

Moderna COVID-19 Vaccine is provided as a white to off-white suspension for intramuscular injection. Each 0.5 mL dose of Moderna COVID-19 Vaccine contains 100 mcg of nucleoside- modified messenger RNA (mRNA) encoding the pre-fusion stabilized Spike glycoprotein (S) of SARS-CoV-2 virus.

Each dose of the Moderna COVID-19 Vaccine contains the following ingredients: a total lipid content of 1.93 mg (SM-102, polyethylene glycol [PEG] 2000 dimyristoyl glycerol [DMG], cholesterol, and 1,2-distearoyl-sn-glycero-3-phosphocholine [DSPC]), 0.31 mg tromethamine, 1.18 mg tromethamine hydrochloride, 0.043 mg acetic acid, 0.20 mg sodium acetate trihydrate, and 43.5 mg sucrose.

Moderna COVID-19 Vaccine does not contain a preservative.

The vial stoppers are not made with natural rubber latex.

### 6.2.3 PRODUCT STORAGE AND STABILITY

During storage, minimize exposure to room light.

The Moderna COVID-19 Vaccine multiple-dose vials are stored frozen between -50° to -15°C (-58° to 5°F). Store in the original carton to protect from light.

Do not store on dry ice or below -50°C (-58°F). Use of dry ice may subject vials to temperatures colder than -50°C (-58°F).

Vials may be stored refrigerated between 2° to 8°C (36° to 46°F) for up to 30 days prior to first use.

Vials may be stored between 8° to 25°C (46° to 77°F) for a total of 24 hours.

After the first dose has been withdrawn, the vial should be held between 2° to 25°C (36° to 77°F). Vials should be discarded 12 hours after the first puncture.

Thawed vials can be handled in room light conditions.

Do not refreeze once thawed.

